# **4** General Issues for Statistical Analysis

### 4.1 Multiplicity, Multiple Comparisons and Interim Analyses

All tests and reported p-values will be two-sided, where a p-value of < 0.05 will be considered to be statistically significant. Estimates will be presented with 95% confidence intervals. There will be no formal adjustment for multiple significance testing. The outcomes however, are clearly categorised by the degree of importance (primary and secondary). No formal interim analyses were planned.

### 4.2 Analysis Software

All data manipulations, tables, figures and analyses will be performed using Stata version 15.0^12. The validated program code (do file) and any other outputs created shall be documented and archived together.

### 4.3 GENEActiv data processing

All GENEActiv data will be processed by the physical activity team prior to statistical analysis. To be included in an analysis a participant needs to provide at least one valid days of GENEActiv data.

# 4.4 Demographic and Baseline Characteristics

Demographic and baseline characteristics for individual participants will be summarised by randomisation group. Numbers (with percentages) for binary and categorical variables and means (and standard deviations), or medians (with lower and upper quartiles) for continuous variables will be presented. The number of missing values will be reported in the footnote of the summary table. There will be no tests of statistical significance nor confidence intervals for differences between randomised groups on any of the baseline variables.

# 4.5 Primary Endpoint Analysis

### 4.5.1 Primary Analysis of Primary Endpoints

The primary outcome is change in overall volume of physical activity (average acceleration, ENMO) from baseline to 12 months. For the primary outcome treatment arm will be compared using linear regression modelling with

1. a binary indicator for randomisation group as the explanatory variable

2. terms for stratification factors (gender and ethnicity) as confounders

3. adjustment for the change from baseline in accelerometer wear time and baseline overall volume of physical activity.

The primary analysis at 12 months will be based on complete data.

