### 1.2.2 Randomisation

Participants will be randomised 1:1; stratified by gender (male; female) and ethnicity (White European; other) to either intervention or control groups.

If two people are taking part from the same household they will be randomised to the same arm to prevent contamination taking place.

Both control and intervention participants will be informed of the outcome of the randomisation. In addition intervention participants will be sent a letter confirming the date and the venue of the education sessions.

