### 1.2.4 Inclusion Criteria

Patients will be included in the study based on the following criteria:

- Good understanding in written and verbal English;
- Able to give informed consent;
- 40-85 years old inclusive;
- Have two or more chronic conditions (see *table1* in MAP protocol v6;20.6.2018)
- Have access to a mobile phone for use in potential study activities;
- Able to walk independently;

There are no limitations with disease duration, medication use and/or initiation of new treatment unless there are specific recommendation for bed rest and minimising physical activity for a specific condition.

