# 2 Outcome Measures

### 2.1 Primary outcome measures

The primary outcome measure is change in overall volume of physical activity measured using accelerometer between baseline and 12 months.

A complete case population will be used for the primary analysis. This will be followed by sensitivity analyses which will include an intention to treat (ITT) population by imputing missing data to assess the robustness of the findings to missing data.

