# 4.7 Subgroup Analyses

We will conduct the following subgroup analyses to assess if the intervention effect is statistically different between these groups.

- Age
- Sex
- Median number of comorbidities
- Depression
- Arthritic condition
- Cardiovascular condition
- Type 2 diabetes
- Physical activity; low and high

The main analysis for each subgroup will involve using the same analytic principles as the primary analysis, but stratifying by the subgroup to estimate the mean difference in the overall volume of physical activity when compared to the control group. Further subgroup analyses will investigate the interaction effects between the treatment and subgroup, this will include an additional interaction term to the model; 'subgroup × treatment'. Subgroup results will be graphically presented as forest plots, with the estimated difference of overall volume of physical activity between treatment groups with 95% confidence interval for the interaction.

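### With about 40% of primary outcomes expected to be missing, neither the primary model nor the imputation uses age or number of chronic conditions: a modest, cheap improvement, not an error

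*SAP*

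**What the plan says.** SAP 4.5.1 specifies a linear regression of change in average acceleration from baseline to 12 months. The terms are the arm indicator, "terms for stratification factors (gender and ethnicity) as confounders", and "adjustment for the change from baseline in accelerometer wear time and baseline overall volume of physical activity". The analysis set is stated twice: "A complete case population will be used for the primary analysis" (2.1) and "The primary analysis at 12 months will be based on complete data" (4.5.1).

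The covariates follow the randomisation strata in 1.2.2: "Participants will be randomised 1:1; stratified by gender (male; female) and ethnicity (White European; other". Age and number of conditions were not strata.

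Both variables appear elsewhere in the SAP. Section 1.2.4 sets the age range as "40-85 years old inclusive" and requires that participants "Have two or more chronic conditions". Section 4.7 lists age and "Median number of comorbidities" as subgroup factors.

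The imputation in 4.5.2.2 predicts activity at baseline and at 12 months from arm, sex and ethnicity only, and then refits the primary model. The per-protocol analysis in 4.5.2.1 also follows the primary model's steps.

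**The concern.** A complete-case regression estimates the treatment effect without bias when missingness depends only on arm and on covariates in the model. With some 40% of outcomes expected to be missing, the covariate list carries much of the missing-data assumption. SAP 3.1 itself names missing values as a potential source of bias.

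Age, over a 45-year range, and burden of disease are natural candidates to influence both return at 12 months and change in activity. One arm is invited to four education sessions (1.2.3), so a dropout relation that differs by arm is conceivable. If it did differ, completers in the two arms would differ on a predictor of the outcome, and part of that difference would enter the treatment coefficient.

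No other planned overall estimate covers this. The imputation and per-protocol analyses condition on neither variable, and the subgroup analyses stratify or test interactions without giving an adjusted overall effect.

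**Working it through.** **Inputs from SAP 1.2.6 and 4.1.** Difference 2.1 mg, SD 5.3 mg, 80% power, two-sided 5%, 20% loss to follow-up plus 20% monitor non-compliance, 202 evaluable, 338 recruited.

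**The plan's own figures.** The normal formula gives n per arm = 2 × (1.96 + 0.84)² × 5.3² / 2.1², about 100. The t-test version gives 100.96, hence 101 per arm and 202 in total. Adding the two losses gives 101 / (1 − 0.40) = 168.3, hence 169 per arm and 338. Both stated figures reproduce. The calculation takes no credit for any covariate.

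**Precision.** The documents give no prognostic strength for either variable, so the partial R² beyond the existing covariates is an assumption. SE = 5.3 × √(1 − R²) × √(2/101):

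| Assumed R² | SE (mg) | Power for 2.1 mg |
|---|---|---|
| 0 | 0.746 | 80.4% |
| 1% | 0.742 | 80.8% |
| 2% | 0.738 | 81.2% |
| 5% | 0.727 | 82.4% |
| 10% | 0.708 | 84.3% |

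Simulated trials of 338 with about 60% complete and no dropout dependence gave SE reductions of 0.3% (R² 1%), 1.2% (3%), 2.4% (5%) and 4.8% (10%).

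**Bias, dependence in the intervention arm only.** Assumptions: 338 randomised, about 60% complete, true effect 2.1 mg, residual SD 5.3 mg, one standardised covariate standing for age or burden, 4,000 trials per cell. Entries are bias in mg with the covariate omitted / adjusted for:

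| R² | Log-odds of dropout 0.5 per SD | Log-odds 0.8 per SD |
|---|---|---|
| 1% | 0.08 / −0.02 | 0.14 / −0.01 |
| 3% | 0.17 / −0.01 | 0.26 / −0.01 |
| 5% | 0.23 / 0.01 | 0.32 / −0.01 |
| 10% | 0.32 / 0.00 | 0.50 / 0.01 |

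Hand check: bias ≈ 5.3 × √R² × gap between completers in SD. The gap is 0.19 SD at log-odds 0.5 and 0.29 SD at 0.8. At R² 3% with 0.19, 5.3 × 0.173 × 0.19 = 0.17 mg. At R² 10% with 0.29, 5.3 × 0.316 × 0.29 = 0.49 mg. Both agree with the simulation.

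**Bias under other dropout patterns.** One simulated population of 4 million per cell, covariate omitted, odds ratio (OR) of dropout per SD:

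| Pattern | R² 2% | R² 5% | R² 10% |
|---|---|---|---|
| OR 1.5 in both arms, 40% missing in each | −0.003 | −0.008 | −0.001 |
| OR 1.5 in both, 35% control, 45% intervention | 0.044 | 0.045 | 0.065 |
| OR 1.0 control, 1.5 intervention, 40% each | 0.112 | 0.181 | 0.272 |
| OR 1.0 control, 2.0 intervention, 40% each | 0.197 | 0.298 | 0.412 |

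Adjusting for the covariate brought every cell to within 0.015 mg of zero. The Monte Carlo standard error is about 5.3 × √(4 / 2.4 million) = 0.007 mg.

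**The case against.** The strongest reply is that 4.5.1 is a standard pre-specified model, with arm, the stratification factors and the baseline value of the outcome. Nothing in the SAP contradicts it. That stands: the omission is an improvable choice, not an error.

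Four stronger readings are tempting, and the documents do not support them.

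- A reader might infer that any dropout related to age or burden biases the comparison. It does not. The dependence or the dropout rates must differ by arm, and the covariate must predict change beyond baseline activity, which may already carry much of its signal.
- A reader might take 0.5 mg as the expected bias. It is the top of an assumed range, with dependence in one arm, none in the other, and R² of 10%. It also applies that selection to the whole 40%, although 1.2.6 attributes half of this to monitor non-compliance, which the burden of attending sessions need not affect.
- A reader might infer a loss of planned power. The sample size relies on no covariate, so there is none.
- A reader might infer from eligibility that the condition count is known for everyone. Section 1.2.4 sets a threshold of two, which can be confirmed without a full count. Medical history (2.2) and the subgroup in 4.7 suggest a count can be obtained, but the SAP does not say it is complete.

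Inclusion in 4.7 concerns effect modification and does not show that either variable is prognostic. Choosing these two from that list is a judgement.

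What survives the objection is that no planned overall estimate, including the missing-data sensitivity analysis, uses either variable.

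**Conclusion.** The point holds as a modest improvement. Its firmest part concerns the imputation model: a sensitivity analysis meant to test robustness to missing data conditions on no more baseline information about participants than two stratification factors, so it cannot reveal or correct selection on age or burden.

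The precision forgone is about 0.3-5% of the standard error for an assumed R² of 1-10%. Uncorrected bias is about zero with equal dependence and equal rates, and 0.04-0.07 mg with equal dependence but 35% against 45% missing. Under assumed one-arm dependence it is about 0.1-0.5 mg, which is 0.08/2.1 = 4% to 0.50/2.1 = 24% of the target difference, against a standard error of about 0.74 mg. The positive sign reflects the assumed direction, in which participants likely to do worse leave the intervention arm. All these sizes rest on assumed prognostic strength and dropout patterns, because the SAP gives neither.

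**What to change.** Amend the SAP before database lock, as its Introduction allows, and before outcomes are seen by arm.

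1. In 4.5.1, pre-specify age (continuous, in years) and number of chronic conditions at baseline as additional covariates. If the sponsor prefers to keep the primary model unchanged, the minimum is a pre-specified sensitivity version of it with both covariates.
2. In 4.5.2.2, add both variables to the imputation equations whichever option is chosen.
3. Confirm that the condition count is recorded for all participants. Under the by-analysis exclusion rule in 3.2, a missing count would otherwise remove a participant from any model that uses it.

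The cost is SAP wording and two degrees of freedom. If neither variable is prognostic beyond baseline activity, there is little gain. The change addresses selection on these observed covariates only, not missingness that depends on the unseen outcome.

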### 4.5.2 Sensitivity Analyses

#### 4.5.2.1 Per Protocol Population

For the PP analysis, participants who have engaged with at least one group session of the programme will be included. The PP will adhere to the same steps as the primary analysis.

#### 4.5.2.2 Intention-to-treat Population

To allow for full analysis set, missing data will be imputed using a multiple imputation procedure which substitutes predicted values from a regression equation. The imputation will be carried out by the MI command in Stata . MI replaces missing values with multiple sets of simulated values to complete the data, performs standard analysis on each completed dataset, and adjusts the obtained parameter estimates for missing-data uncertainty using Rubin's rules to combine estimates .

The following procedure will be followed:

- The MI will be set as wide
- The MI will register imputation of the overall volume of physical activity at 12 months and at baseline
- A regression method will be used , where the registered variables will be individually adjusted for the randomisation and stratification factors (sex and ethnicity), with 100 imputations to avoid biased estimates, rseed (2259) and the force options
- MI estimate will provide the final results using the same regression model as the primary analysis and covariate adjustments.

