# 3.2 Complete Case Population

The level of missing data for each outcome will be assessed. If missing outcome data is present the initial analysis will be based on the complete cases. All tests of the effect of treatment on outcomes will be conducted on a complete case (CC) population. That is, all the recruited participants will be included in the analysis, with the exception of those with missing outcome data. This will be done on a 'by analysis' basis, i.e. only those participants with missing data for variables required for a specific analysis will be removed.

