# 3.3 Intention-to-treat Population/Full analysis set

The intention-to-treat (ITT) analysis population will consist of all participants randomised. Participants will be analysed in the group to which they were randomly allocated and regardless of any protocol deviations or violations. Multiple imputation methods will be used to impute missing outcome data. This will be a sensitivity analysis.

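### The multiple-imputation analysis does not impute change in wear time, which its own regression model needs, so participants lost by 12 months drop out of the analysis meant to include them

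*SAP*

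**What the plan says.** Section 3.3 of the SAP defines the population: "The intention-to-treat (ITT) analysis population will consist of all participants randomised". It adds: "Multiple imputation methods will be used to impute missing outcome data". Section 4.5.2.2 gives the aim and the steps. The aim is: "To allow for full analysis set, missing data will be imputed using a multiple imputation procedure". The variables to be imputed are activity only: "The MI will register imputation of the overall volume of physical activity at 12 months and at baseline". The predictors are arm, sex and ethnicity: "the registered variables will be individually adjusted for the randomisation and stratification factors (sex and ethnicity), with 100 imputations to avoid biased estimates". The model fitted afterwards is the primary one: "MI estimate will provide the final results using the same regression model as the primary analysis and covariate adjustments".

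Section 4.5.1 lists what that model contains. Besides arm, gender and ethnicity, it has "adjustment for the change from baseline in accelerometer wear time and baseline overall volume of physical activity".

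Sections 2.1 and 3.1 say that sensitivity analyses are there to assess robustness to missing data. Section 3.1 also excludes from all analyses anyone who did not attend the baseline assessment after consent.

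**The concern.** Change in wear time can be computed only from accelerometer recordings at both visits. It is therefore missing for everyone lost by 12 months, and for anyone without a baseline recording. These are people whose activity the procedure sets out to impute. A linear regression drops any row with a missing covariate, and wear time is missing for the same rows in every completed dataset. For these people the imputed activity value never enters the fit.

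The stake is the SAP's check on its own complete-case primary analysis. The per-protocol population (section 3.4) also requires complete data, so the imputed analysis is the only planned one that handles missing outcomes. If it silently loses the people lost to follow-up, it does not do the job that sections 2.1, 3.3 and 4.5.2.2 give it.

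**Working it through.** **Inputs.** From section 1.2.6: difference 2.1 mg, SD 5.3 mg, power 80%, significance level 5%, 202 evaluable, 20% loss to follow-up, 20% monitor non-compliance, 338 recruited (169 per group). From section 1.2.2: 1:1 allocation. From section 4.1: two-sided tests.

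**1. The plan's own figures reproduce.**
- Normal approximation: 2 × (1.960 + 0.842)² × (5.3/2.1)² ≈ 100 per arm.
- t-test version: 100.96, so 101 per arm, or 202 in total, as stated.
- Inflation with the two allowances added: 101 / (1 − 0.40) = 168.3, so 169 per arm, or 338, as stated.

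**2. What each step of the imputation plan covers.**

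| Variable in the post-imputation model | Known for all randomised? | Imputed under section 4.5.2.2? |
|---|---|---|
| Arm, gender, ethnicity | Yes (allocation and stratification) | Not needed |
| Baseline activity | Not always | Yes |
| 12-month activity (through the change) | No | Yes |
| Change in wear time | No | No |

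The last row is the gap. The force option named in the procedure does not impute a variable that has not been registered.

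**3. How many are affected at planning rates.**
- Lost to follow-up: 338 × 0.20 = 67.6, about 68. They have no 12-month wear time.
- Lost plus non-compliant: 338 − 202 = 136 (338 × 0.40 = 135.2).
- The imputed analysis would therefore be fitted to between 338 − 68 = 270 participants (every non-complier has wear time at both visits) and 338 − 136 = 202 (none has).

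**4. Illustration.** One dataset of 338 was simulated with 12-month activity missing at random with probability 40%, baseline complete, 100 imputations and Rubin's rules, using the SAP's imputation predictors and its analysis model. The baseline mean and spread and the wear-time effect are assumptions.

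| Scenario | N fitted | Estimate (mg) | SE |
|---|---|---|---|
| Complete case | 203 | 1.1556 | 0.8126 |
| Imputation as planned, wear time missing whenever activity is | 203 | 1.1556 | 0.8126 |
| Imputation as planned, about half of those missing activity have wear time (assumption) | 277 | 0.4353 | 1.2192 |
| Change in wear time also imputed | 338 | 0.1838 | 1.3018 |

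The first two rows are identical because no imputed value enters the fit; that does not depend on the assumed values. The third row would average 338 × 0.80 ≈ 270; this draw gave 277. The estimates and SEs in the last two rows come from a single dataset and say nothing about which approach is better. They show only that the result can move once imputed rows are used.

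**The case against.** **A reader might infer that the imputed analysis always collapses to the complete-case analysis.** The SAP does not support that. It does not define wear time or say how it is recorded when a monitor is hardly worn. Section 1.2.6 separates loss to follow-up from monitor non-compliance, and section 4.3 requires at least one valid day. A participant who returned a monitor with too little wear may have a recorded wear time and would stay in the model with imputed activity. The two analyses would then differ. This part of the objection stands, and it is why the size is a range. It does not bring back anyone lost to follow-up.

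**Missing 12-month wear time could be coded as zero.** That would keep the rows, but the SAP does not say so. Section 4.5.2.2 goes down to the seed and the software options, so this is a stated procedure that fails its purpose rather than a detail left open.

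**A reader might also infer that the result will be cited as proof of robustness.** No section says what will be concluded, and the fitted N is an ordinary output in which the shortfall would show. The sound point is narrower: the procedure as written cannot deliver its stated population.

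**It is only a sensitivity analysis.** True: the primary estimate, its p-value and its sample size are untouched. Against that, it is the only planned analysis that handles missing outcomes, in a trial that allows for 40% of them.

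**Conclusion.** The point holds. As written, the analysis described as covering all randomised participants leaves out everyone lost by 12 months, contrary to sections 3.3 and 4.5.2.2. At planning rates that is about 68 of 338 (20%), rising to about 136 (40%) if monitor non-compliers also lack wear time. Equality with the complete-case result is exact only at the upper end, where activity and wear time are always missing together; there the analysis gives no information on robustness to missing data.

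This rests on two assumptions: that missing wear time is left missing rather than set to a value, and that the section 1.2.6 allowances describe the missingness that occurs. Observed rates may differ and would change the counts but not the mechanism.

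**What to change.** Pre-specify one of two options in section 4.5.2.2, before database lock:

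- **(a)** Register wear time at both visits (or its change) and impute it jointly with activity, keeping the primary model. The line that predicts each variable separately from arm, sex and ethnicity would be reworded to match.
- **(b)** Fit the imputed analysis without the wear-time covariate, and also report the complete-case model without it. Without that second model, covariates and population change together and a difference from the primary result could not be attributed to missing data.

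Either restores the sample. Option (a) keeps the imputed and primary models aligned; option (b) avoids imputing wear time for people who did not wear the device.

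In both cases, state the expected N for the imputed analysis as all randomised participants, reconciled with the section 3.1 exclusion of those who did not attend baseline, and check that the fitted N matches it.

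The cost is a few lines of SAP wording and code, plus one extra complete-case fit under (b). No new data are needed, and the primary analysis and sample size do not change.

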### **1.2.6** Sample size calculations

The primary outcome is change from baseline to 12 months average daily physical activity, as quantified by the Euclidean norm minus one (ENMO) method measured in milligravity units (mg). This is the main measure of activity derived from the activity monitor. In order to detect a minimum clinically significant difference of 2.1 mg, which is equivalent to an overall increase in physical activity volume of approximately 30 minutes of light walking at 4km/h, assuming a standard deviation of 5.3 mg [1], a power of 80% and significance level of 5%, the sample size requires 202 participants. To allow for 20% loss to follow-up and 20% non-compliance of the activity monitor, we will therefore need to recruit 338 participants (169 in each group).

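### The imputation model for the ITT sensitivity analysis leaves out two covariates of the model it feeds, so it is either less precise than the complete-case analysis, and open to bias, or close to a repeat of it

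*SAP*

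**What the plan says.** The primary analysis (SAP 4.5.1) is a complete-case linear regression of change in activity on arm, with terms for gender and ethnicity and "adjustment for the change from baseline in accelerometer wear time and baseline overall volume of physical activity".

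Section 3.3 defines the ITT set as everyone randomised and adds "Multiple imputation methods will be used to impute missing outcome data", as a sensitivity analysis. Section 2.1 gives its purpose: to see how robust the findings are to missing data.

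Section 4.5.2.2 gives the recipe. Two variables are registered for imputation, activity at 12 months and at baseline. By a regression method, "the registered variables will be individually adjusted for the randomisation and stratification factors (sex and ethnicity"), with 100 imputations. The primary model, with its covariates, is then fitted to the completed data. Wear time is neither registered for imputation nor listed as a predictor.

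**The concern.** An imputation model should contain at least the variables of the analysis model that follows. Here two are absent.

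- **Baseline activity.** A participant with an observed baseline and no 12-month value receives a 12-month value that, within arm, sex and ethnicity, is unrelated to that baseline. The imputed change is then a group mean plus noise, minus the participant's real baseline. The procedure also assumes that missingness is unrelated to baseline activity given arm, sex and ethnicity. The complete-case model conditions on baseline and does not need that assumption, so the check rests on a stronger assumption than the analysis it checks.
- **Change in wear time.** Participants without 12-month activity data will probably also lack 12-month wear time. If so, they cannot enter the fitted model even after their activity has been imputed.

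This is the only imputation-based check in the SAP, and section 1.2.6 allows for 20% loss to follow-up plus 20% monitor non-compliance. A difference from the primary result could be an artefact of the imputation model. Agreement could mean only that the same participants were analysed twice.

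**Working it through.** **1. Inputs from the SAP.** From section 1.2.6: "minimum clinically significant difference of 2.1 mg", "assuming a standard deviation of 5.3 mg", 80% power, 5% significance, 202 evaluable, 338 recruited (169 per arm). Tests are two-sided (4.1) and allocation is 1:1 (1.2.2).

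**2. The plan's own figure.** n per arm = 2(1.96 + 0.842)² × (5.3/2.1)² ≈ 100, so 200 in total. The exact t-test calculation gives 101 per arm, so 202 (power 80.0%). Then 202/(1 − 0.40) = 336.7, which is 338 after rounding up to equal arms. Both figures reproduce. Missing outcomes are therefore 40% if the two allowances are added, or 1 − 0.8 × 0.8 = 36% if compounded.

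**3. Assumptions, because the SAP gives no figure.** 5.3 mg is taken as the SD of change. The baseline-to-12-month correlation ρ is varied from 0.5 to 0.8. Missingness is about 36% at 12 months and 5% at baseline. The SD at each visit is then s = 5.3/√(2(1 − ρ)). Wear time is left out of the simulated model, which amounts to assuming that it is available for everyone.

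**4. Lost association.** Imputed values carry no link between the visits, so the slope of 12-month on baseline activity should shrink to about ρ × 0.64 × 0.95 = 0.608ρ. That is 0.30, 0.43 and 0.49 for ρ = 0.5, 0.7 and 0.8. Simulation (400 trials per scenario, 15 imputations, missing completely at random) gave 0.30, 0.43 and 0.48. Joint imputation recovered 0.50, 0.70 and 0.80.

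**5. Precision, missing completely at random, true effect 2.1 mg.** The complete-case SE is about 2s√(1 − ρ²)/√n with n = 338 × 0.64 × 0.95 = 205.5, which gives 0.66 at ρ = 0.6 and 0.69 at ρ = 0.75. Mean simulated results:

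| ρ | SE, complete case | SE, joint imputation | SE, as written | Power, joint | Power, as written |
|---|---|---|---|---|---|
| 0.5 | 0.64 | 0.64 | 0.71 | 0.91 | 0.82 |
| 0.7 | 0.69 | 0.69 | 0.89 | 0.85 | 0.68 |
| 0.8 | 0.71 | 0.71 | 1.09 | 0.86 | 0.47 |

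Simulated trials at ρ = 0.6 and 0.75 gave 0.79 to 0.97 as written against 0.66 to 0.70, a ratio of 0.79/0.66 = 1.20 to 0.97/0.70 = 1.39.

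**6. Bias in the treatment effect (true 2.1 mg), imputation as written, ρ = 0.5, 0.7, 0.8.**

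- Missing completely at random: 2.08, 2.11, 2.10. No bias.
- Missingness depends on baseline equally in both arms: 2.15, 2.00, 2.19, with coverage 94 to 97%. No bias.
- Missingness depends on baseline in opposite directions by arm, a deliberately strong case: 3.52, 4.51, 5.64, with coverage 49%, 21% and 5%. Complete case stays at 2.06 to 2.12 and joint imputation at 2.13 to 2.20.
- Milder case, true effect zero, less active participants more often missing in the intervention arm only, ρ = 0.6 and 0.75: about +0.9 to +1.5 mg, with 20 to 32% rejection. Complete case and joint imputation stay near 0 mg and 4 to 5%.

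**7. How strong are these mechanisms?** Each arm's imputed mean is its observed mean, so bias ≈ ρ × s × d, where d is the between-arm difference, in SD units, in mean baseline activity among those with 12-month data. In the strong case d = 1.42/2.65 = 0.54, 2.41/4.79 = 0.50 and 3.54/6.70 = 0.53. In the one-arm case d = 0.9/3.56 = 0.25 and 1.5/5.62 = 0.27. So a bias of that size needs about a quarter of an SD of baseline imbalance among those followed up.

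**8. Wear time.** If it is missing whenever 12-month activity is missing, the model in section 4.5.1 can use only participants with both. Steps 4 to 7 then do not arise, and the ITT estimate is roughly the complete-case one.

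**The case against.** Four objections deserve weight.

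- **The treatment effect is not generally biased.** A reader might infer that this imputation always distorts it. The documents do not support that. Randomisation makes baseline activity independent of arm, and step 6 shows no bias unless missingness relates to baseline activity differently by arm. The SAP does not predict such dropout. It is possible, since participants know their allocation (1.2.2) and only one arm is invited to sessions (1.2.3), but it remains an assumption. This objection stands, and the point is worded to match.
- **The simulated harm assumes that wear time is available.** This also stands. The SAP does not say how wear time is recorded for someone without 12-month data. The alternative is no defence of the plan, because the ITT analysis then leaves out the participants it was meant to bring in.
- **The wording does not fix the command.** A chained-equations command could let each activity variable predict the other. But the stated predictor list is arm, sex and ethnicity, and separate regressions are the natural reading of a variable-by-variable adjustment. If joint imputation was intended, the text needs to say so.
- **It is only a sensitivity analysis.** Correct. A reader might take the power figures above as a loss of trial power. They are not: the primary estimate, its power and its type I error are untouched, and no rule in the SAP ties the conclusion to the imputed result.

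**Conclusion.** The point holds in a conditional form, at moderate severity. The imputation model as written omits baseline activity and change in wear time, both of which are in the analysis model.

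- **If wear time is available for imputed participants**, the ITT analysis has an SE of about 0.79 to 0.97 against 0.66 to 0.70 for complete case (ρ = 0.6 to 0.75). It can be biased, by about +0.9 to +1.5 mg under a true null in the assumed one-arm mechanism, but only if missingness relates to baseline activity differently by arm.
- **If wear time is missing along with the 12-month data**, the ITT analysis is roughly the complete-case analysis under another name.

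In neither case does it do the job that section 2.1 gives it. The sizes rest on the assumed correlation, the assumed missingness rates and mechanisms, and on reading 5.3 mg as the SD of change. The direction of the precision loss was the same at every correlation tried.

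**What to change.** Rewrite the procedure in section 4.5.2.2 as follows:

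1. Register baseline activity, 12-month activity and wear time at both visits.
2. Impute them jointly, by chained equations or a multivariate normal model, each conditional on the others and on arm, sex and ethnicity.
3. Derive change in activity and change in wear time after imputation, then fit the model of section 4.5.1.
4. If wear time cannot sensibly be imputed for people who did not wear the monitor, drop that adjustment from the imputed analysis and say so.
5. State how many participants enter the fitted model, so that it is clear the full randomised set is analysed.

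Adding baseline predictors of activity or dropout (for example age, BMI or number of conditions) and imputing within arm are optional refinements.

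The cost is a paragraph of SAP wording and a few lines of code. No new data are needed, and the primary analysis does not change.
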